## 12.6 Safety Analyses

The safety endpoints are:

- AEs
- Biomicroscopy findings
- Device deficiencies

There are no safety hypotheses planned in this study. The focus of the safety analysis will be a comprehensive descriptive assessment of occurrence of adverse events as well as the other listed parameters.

All AEs occurring from the time a subject signs informed consent to study exit will be accounted for in the reporting. Safety analyses will be conducted using the safety analysis set on a treatment-emergent basis. Descriptive summaries (frequencies and percentages) for ocular and nonocular AEs will be presented by Medical Dictionary for Regulatory Activities Preferred Terms. AEs leading to study discontinuation, significant nonserious AEs, and SAEs will be identified. Individual subject listings will be provided, as necessary.

Individual subject listings will be provided for AEs that occur after signing informed consent but prior to exposure to IP.

Each biomicroscopy parameter will be tabulated by its grade. For each biomicroscopy parameter, frequencies and percentages of eyes that experience an increase of  $\geq 2$  grades from baseline (last assessment prior to study lens exposure) to any subsequent visit within the same period will be presented. A supportive listing will be generated which will include all biomicroscopy data from all visits within the same period for those eyes experiencing the  $\geq 2$  grades increase.

Two listings for device deficiencies, prior to exposure to study contact lenses and treatment-emergent, will be provided. Additionally, each device deficiency category will be tabulated.

No inferential testing will be conducted for the safety analyses.

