## 10.5.2 Discontinuations

Discontinued subjects are individuals who voluntarily withdraw or are withdrawn from the study by the investigator after signing informed consent and after randomization.

Subject numbers of discontinued subjects must not be reused (i.e., subject replacement is not allowed).

Subjects may discontinue from study or study treatment at any time for any reason. Subjects may also be discontinued from study treatment at any time if, in the opinion of the investigator, continued treatment poses a risk to their health.

If a subject discontinues from study treatment, every effort must be made to keep the subject in the study and to continue with the study assessments as specified in the schedule of study procedures and assessments until the final visit.

For subjects discontinuing from the study, the investigator must complete all Exit procedures according to [Table 3–1](#) and [Section 10.5.3](#), if the subject is willing and able, and if in the opinion of the investigator it is safe for the subject to do so.

The investigator must document the reason for study or treatment discontinuation in the subject's case history source documents.

To ensure the safety of all subjects who discontinue early, investigators must assess each subject and, if necessary, advise them of any therapies and/or medical procedures that may be needed to maintain their health.

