### ***Significant Nonserious Adverse Events***

A significant nonserious AE is a device-related, non-sight threatening adverse event that warrants discontinuation of any contact lens wear for greater than or equal to 2 weeks. In addition, the investigator must report any occurrences of the following as a significant nonserious adverse event:

- Peripheral nonprogressive noninfectious ulcers
- All symptomatic corneal infiltrative events

Corneal staining score greater than or equal to grade 3 (Refer to MOP for grading scales)

- Temporary vision loss as defined by loss of 2 or more lines of BCVA from baseline visit that persists for 2 or more weeks

Neovascularization score greater than or equal to grade 2 (Refer to MOP for grading scales)

*The above events are based on the categories provided in the ISO 11980 and the US FDA Premarket Notification (510[k]) Guidance Document for Daily Wear Contact Lenses and Contact Lens Care Products.*

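### Section 12.6 identifies AEs that lead to leaving the study, but has no category for nonserious AEs that make a retained subject give up one study lens

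*Protocol*

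**What the plan says.** Protocol section 12.6 singles out three classes of adverse event: "AEs leading to study discontinuation, significant nonserious AEs, and SAEs will be identified". The same section also commits to full reporting: "All AEs occurring from the time a subject signs informed consent to study exit will be accounted for in the reporting", with frequencies and percentages by Preferred Term. Section 12.2.1 assigns subjects and eyes to the lens to which they were actually exposed.

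Section 10.5.2 recognises two kinds of stopping: "Subjects may discontinue from study or study treatment at any time for any reason". It defines the discontinued subject by departure from the study: "Discontinued subjects are individuals who voluntarily withdraw or are withdrawn from the study by the investigator after signing informed consent and after randomization". Its provision for a stop on health grounds acts on study treatment, not on study participation. For those who stop treatment it adds: "If a subject discontinues from study treatment, every effort must be made to keep the subject in the study", with scheduled assessments continuing to the final visit. On documentation: "The investigator must document the reason for study or treatment discontinuation in the subject's case history source documents".

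Two neighbouring sections also bear on this. Section 10.3 sends a subject who is stopping the investigational product at an Unscheduled Visit to Exit procedures, just as it does a subject who is leaving the study. Section 10.5.3 is headed for subjects discontinued from the investigational product, but its body speaks only of subjects who discontinue from the study and gives them an Early Exit Visit.

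**The concern.** The discontinuation class in 12.6 is tied to one of the two events that 10.5.2 distinguishes, and it is the one that says less about the product. The safety objective is to describe the safety profile of the study products. In a two-lens crossover, an AE that made the subject stop a particular lens is a result about that lens. Leaving the study also reflects the subject's circumstances and the site's effort to retain them.

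If the flag follows study exit only, a reader of the report who wants to know how often an AE ended wear of each lens will not find the answer in the class that appears to give it. Two subjects with the same AE and the same decision to stop the lens can be classified differently because one site exited the subject and the other kept the subject in follow-up.

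**Working it through.** **Step 1. Which AEs fall outside the three classes?** Take an AE that ends wear of one study lens and apply each class in turn.

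- *SAE* (Glossary and 11.1): applies only if the event meets the seriousness definition or is on the additional list in 11.1.
- *Significant nonserious AE* (11.1): a device-related, non-sight-threatening "adverse event that warrants discontinuation of any contact lens wear for greater than or equal to 2 weeks", plus listed events such as symptomatic corneal infiltrative events, peripheral noninfectious ulcers, corneal staining of grade 3 or more and neovascularization of grade 2 or more.
- *AE leading to study discontinuation* (12.6): applies only if the subject leaves the study.

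A nonserious AE that is off the lists, does not call for two weeks without any lens, and occurs in a subject who stays in follow-up meets none of these. Discomfort or poor vision reported as an AE that ends wear of one lens would be an example.

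**Step 2. Does the text settle whether such a subject stays or leaves?**

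| Section | Subject who stops the lens |
|---|---|
| 10.5.2 | Every effort to retain, with assessments to the final visit |
| 10.3 | Exit procedures, if the stop occurs at an Unscheduled Visit |
| 10.5.3 | Heading covers this subject; body addresses study discontinuation only |

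A site that follows 10.3 may exit the subject, and the AE is then flagged. A site that follows 10.5.2 retains the subject, and the same AE is not flagged.

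**Step 3. Scale.** The protocol's only figures on discontinuation are in section 8: about 82 enrolled, 74 completed, about 5% screen failure and 5% discontinuation. They agree with each other:

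- 74 / (0.95 × 0.95) = 81.99, or 82 enrolled.
- Randomised: 82 × 0.95 = 77.9, about 78.
- Allowed discontinuations: 77.9 × 0.05 = 3.9, about 4.
- One subject: 1/78 = 1.3 percentage points.

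The protocol gives no rate of AE-related lens stops, so the following is an illustration on assumed inputs. Let k subjects stop a given lens because of an AE outside the other two classes, and let a share s of them be retained. The flag in 12.6 shows k(1 − s); a flag on lens discontinuation shows k. The denominator is taken as all 78 randomised.

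| k (assumed) | s = 0 | s = 0.5 | s = 1 | Lens-stop flag, any s |
|---|---|---|---|---|
| 2 | 2 (2.6%) | 1 (1.3%) | 0 (0%) | 2 (2.6%) |
| 4 | 4 (5.1%) | 2 (2.6%) | 0 (0%) | 4 (5.1%) |

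**The case against.** Four arguments can be made against the point.

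*Nothing is lost from the AE count.* This is correct. A reader might infer that AEs which stop a lens disappear from the safety report. The protocol does not support that: 12.6 accounts for all AEs from consent to exit by Preferred Term, and 12.2.1 places them under the lens actually worn. Only the discontinuation label is missing.

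*The other two classes cover much of the ground.* They do cover serious events, device-related events needing two or more weeks without lenses, and the listed corneal findings. What remains uncovered is the milder nonserious AE that still ends wear of one lens.

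*Retention is a best effort, and 10.3 and 10.5.3 may turn a lens stop into an exit.* This also stands, and it rules out the inference that good compliance with 10.5.2 drives the flagged count to zero. But it confirms that the count depends on which section a site follows.

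*The SAP, which is not at hand, could add the row.* It could, and nothing in 12.6 forbids it. However, 12.6 is not silent here: it names a discontinuation class and sets it by study exit.

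A reader might also infer from the source-document sentence in 10.5.2 that the database cannot identify lens stops. That is not established. The sentence covers both kinds of stopping equally, Table 3-1 provides an Exit form, and the MOP and the eCRF are not shown.

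**Conclusion.** The point holds as a minor one. Section 12.6 fixes a discontinuation class that is too narrow for a per-lens safety description in a crossover, given the distinction in 10.5.2. A nonserious AE that ends wear of one lens in a retained subject, and that is not a significant nonserious AE, is summarised by Preferred Term but not identified as leading to discontinuation.

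How many AEs this would affect cannot be determined from the protocol. The 5% allowance in section 8 is for discontinuation from any cause and does not size the gap. The firm part is the unit: about 1.3 percentage points of the flagged rate per retained lens-stopper, with about 78 randomised as the denominator. The values of k and s in the illustration are assumptions.

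Safety reporting in this trial is descriptive, with no hypotheses. The primary noninferiority test, the sample size and the analysis sets are unaffected.

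**What to change.** 1. In 12.6, replace the first of the three classes with: *AEs leading to discontinuation of a study lens and AEs leading to study discontinuation, each by the lens worn at onset.* Keep the other two classes as they are.
2. Confirm that the eCRF records which lens was stopped and why, in addition to the source documents. If it already does, no change is needed.
3. Reconcile 10.3, 10.5.2 and 10.5.3 so that they say the same thing about a subject who stops the investigational product without withdrawing from the study. Which course is right is a matter for the sponsor and the investigators.

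The cost is one extra row in a descriptive AE table, at most a small addition to the eCRF, and a wording edit. The reported number of AE-related lens stops may come out somewhat higher than the study-exit count alone.

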## 8.2 Exclusion Criteria

Subjects fulfilling **any** of the following criteria are not eligible for participation in this study.

1. Any anterior segment infection, inflammation, or abnormality or disease (including systemic) that contraindicates contact lens wear, as determined by the investigator.
2. Any use of systemic or ocular medications for which contact lens wear could be contraindicated, as determined by the investigator.
3. History of refractive surgery or planning to have refractive surgery during the study, or irregular cornea in either eye.
4. Ocular or intraocular surgery (excluding placement of punctal plugs) within the previous 12 months or planned during the study.

5. Biomicroscopy findings at screening that are moderate (Grade 3) or higher and/or corneal vascularization that is mild (Grade 2) or higher, and/or the presence of corneal infiltrate.
6. Current or history of pathologically dry eye in either eye that, in the opinion of the investigator, would preclude contact lens wear.
7. Current or history of herpetic keratitis in either eye.
8. Eye injury in either eye within 12 weeks immediately prior to enrollment for this trial.
9. Current or history of intolerance, hypersensitivity, or allergy to any component of the study products.
10. Currently pregnant or lactating, as stated by subject at Screening.
11. Any history of amblyopia, strabismus, or binocular vision abnormalities.
12. Any use of topical ocular medications and artificial tear or rewetting drops that would require instillation during contact lens wear.
13. The investigator, his/her staff, family members of the investigator, family members of the investigator's staff, or individuals living in the households of the aforementioned persons may not participate in the study.
14. Participation of the subject in a clinical trial within the previous 30 days or currently enrolled in any clinical trial.
15. Monovision contact lens wearers and wearers of contact lens in one eye only.
16. Wearing habitual contact lenses in an extended wear modality (routinely sleeping in lenses for at least 1 night per week) over the last 3 months prior to enrollment.

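### The two-grade rule in Section 12.6 leaves out of the biomicroscopy change table and listing eyes that rise one grade to the protocol's own significant-event thresholds

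*Protocol*

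**What the plan says.** Three parts of the protocol bear on this point.

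- **Section 12.6, Safety Analyses.** Each biomicroscopy parameter is tabulated by grade. A change table then gives "frequencies and percentages of eyes that experience an increase of" two or more "grades from baseline (last assessment prior to study lens exposure) to any subsequent visit within the same period will be presented". The supportive listing is restricted in the same way: it holds "all biomicroscopy data from all visits within the same period for those eyes experiencing the" two-grade increase. The same section says that significant nonserious adverse events will be identified, and promises individual subject listings where necessary.
- **Section 8.2, exclusion criterion 5.** It bars "Biomicroscopy findings at screening that are moderate (Grade 3) or higher", and separately "corneal vascularization that is mild (Grade 2) or higher". Findings up to Grade 2, and vascularization up to Grade 1, are therefore admitted.
- **Section 11.1, Significant Nonserious Adverse Events.** The investigator must report, among others, "Corneal staining score greater than or equal to grade 3" and "Neovascularization score greater than or equal to grade 2 (Refer to MOP for grading scales"). The grading scales themselves are in the manual of procedures, which is not part of the protocol.

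**The concern.** Section 12.6 fixes a single criterion, the size of the change, for both the change table and the eye-level listing. Section 11.1 defines significance by the absolute grade reached. The two need not agree, and here they do not. An eye that enters at the highest admitted grade needs only one step to reach the level the protocol calls significant, and a one-step change is not flagged.

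Biomicroscopy is a safety endpoint in its own right, next to adverse events (Section 6.4). Its graded data are recorded at every visit and could show whether each crossing of a Section 11.1 threshold was also reported as an event. That requires an output that picks out the eye, its starting grade in the period and its grades over visits. The listing is the planned output of that kind, and it omits these eyes.

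**Working it through.** No sample size, power or error-rate figure is involved. The check is an enumeration of grade moves.

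**Inputs**
- Flag rule (Section 12.6): follow-up grade minus period baseline grade is at least 2.
- Highest admitted grade at screening (Section 8.2, criterion 5): staining 3 − 1 = 2; vascularization 2 − 1 = 1.
- Significant-event threshold (Section 11.1): staining 3; neovascularization 2.
- Assumptions: whole-number grades starting at 0, and the same scale for eligibility, follow-up and adverse-event grading. The top of the scale is not given, so 3 and 4 are both tried.

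**Step 1: smallest rise that reaches the threshold, from each admitted grade**

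| Parameter | Starting grade | Threshold | Rise needed | Flagged on reaching the threshold? |
|---|---|---|---|---|
| Staining | 0 | 3 | 3 | yes |
| Staining | 1 | 3 | 2 | yes |
| Staining | 2 | 3 | 1 | **no** |
| Neovascularization | 0 | 2 | 2 | yes |
| Neovascularization | 1 | 2 | 1 | **no** |

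The pattern is structural. For each parameter the grade that excludes a subject at screening is the same as the grade that defines a significant event (3 and 3; 2 and 2). The highest admitted grade is thus always one step below the threshold, and the rule needs two steps.

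**Step 2: all moves from an admitted grade to a grade at or above the threshold**

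| Parameter | Scale | Crossing moves | Not flagged |
|---|---|---|---|
| Staining | 0–3 | 3 | 1 (2→3) |
| Staining | 0–4 | 6 | 1 (2→3) |
| Neovascularization | 0–3 | 4 | 1 (1→2) |
| Neovascularization | 0–4 | 6 | 1 (1→2) |

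On a scale that ends at 3, a staining eye that starts at Grade 2 can never be flagged, because Grade 4 does not exist.

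**Step 3: the reverse case.** Staining 0→2 is a rise of 2, so it is flagged and listed although Grade 2 is below the Section 11.1 threshold. The rule can list a sub-threshold change while omitting a threshold crossing.

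**Step 4: effect of the proposed rule.** With the flag defined as a rise of at least 2, or a grade newly at or above the threshold, the number of crossing moves not flagged is 0 for staining and 0 for neovascularization.

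**Sensitivity.** The moves 2→3 and 1→2 are missed wherever the scale starts or ends. Half-grade steps would add missed moves (2.5→3, for example) and remove none. Eligibility is checked at screening, whereas the analysis baseline is the last assessment before lens exposure, so a baseline could also lie above the screening limit; that does not weaken the result.

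**The case against.** The strongest reply is that these eyes are already covered.

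- **Adverse-event route.** Section 11.1 makes both findings mandatory significant nonserious adverse events, Section 12.6 says such events will be identified, and Section 11.2 has the investigator review changes in protocol-specific parameters. An eye escapes only if a site records the grade and then fails to report it. This stands: the eyes have a reporting category and a planned output.
- **By-grade tabulation.** Staining of Grade 3 and vascularization of Grade 2 are barred at screening, so a count in those rows at a later visit shows by itself that something has appeared since entry. This also stands. A reader might infer from the two-grade rule that such eyes vanish from the safety results altogether; the protocol does not support that.
- **Different purposes.** The change table describes magnitude and Section 11.1 defines absolute levels. Nothing in Section 12.6 says that the table is meant to audit adverse-event reporting, and there are no safety hypotheses. That is fair, so this is not a formal contradiction. Nor is it merely a detail left to the statistical analysis plan, because Section 12.6 itself states the criterion and restricts the listing to it.

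What remains is narrower. The by-grade table gives counts without the eye, its period baseline or its course, and adverse-event listings are promised only as necessary. Neither replaces the eye-level listing.

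A reader might also extend the point to corneal infiltrates, since exclusion criterion 5 treats them as present or absent and such a finding could never rise by two grades. The scoring of infiltrates during follow-up is not shown, so the documents do not establish this.

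**Conclusion.** The point holds in a limited form. Section 12.6 fixes a change rule that fits poorly with the protocol's own thresholds: staining 2→3 and neovascularization 1→2 reach the significant-event level and enter neither the change table nor its listing. The consequence is that the graded data cannot readily confirm, eye by eye, that the corresponding adverse event was reported.

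The size is one missed move per parameter on whole-number scales: 1 of 3 or 1 of 6 crossing moves for staining, and 1 of 4 or 1 of 6 for neovascularization, depending on whether the scale ends at 3 or 4. These count possible moves. A reader might take them as the share of eyes affected, but the protocol gives no grade frequencies and no such estimate can be made.

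The conclusion assumes that staining is among the findings covered by the screening limit, and that eligibility and adverse-event grades share a scale. The primary analysis, the sample size and the duty to report adverse events are untouched. This is a cheap improvement to a descriptive output.

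**What to change.** In Section 12.6, widen the flag for the change table and its listing. By lens and period, include any eye with either (a) an increase of at least two grades from the period baseline, or (b) a post-baseline grade that newly reaches a Section 11.1 threshold, that is corneal staining of Grade 3 or more or neovascularization of Grade 2 or more. Show the two reasons separately, so that the planned two-grade count stays available. Before database lock, cross-check the flagged eyes against the reported significant nonserious adverse events and query any mismatch.

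Leave infiltrates out of the rule unless the scale in the manual of procedures shows that they are scored as present or absent.

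The cost is a little extra table and listing programming and one reconciliation step, on data already collected. The flagged count may be somewhat higher. No new assessment is needed, and the thresholds are those the protocol already states.

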## 12.8 Interim Analyses and Reporting

There are no plans to conduct an interim analysis and no criteria by which the study would be terminated early based upon statistical determination.

## 12.9 Sample Size Justification

Sample size calculation is based on a prior feasibility clinical study (1).

## 13 DATA HANDLING AND ADMINISTRATIVE REQUIREMENTS

## 13.1 Subject Confidentiality

The investigator must ensure that the subject's identity is kept confidential throughout the course of the study. In particular, the investigator must keep an enrollment log with confidential identifying information that corresponds to the subject numbers and initials of each study participant. The study sponsor may collect a copy of the enrollment log ***without any directly identifying subject information.***

The study sponsor may share patient-level data collected in this trial with qualified researchers to help facilitate product development or enhancements in research that is not directly related to the study objectives. The informed consent explains this to the study subject.

